In the event of an SAE, the investigator will send a safety report form within 24 hours of becoming aware of the SAE to:

[REDACTED]

[REDACTED]

[REDACTED]

PROTOCOL SUMMARY

Protocol Number: ATI-450-RA-201

Protocol Title: A Phase 2a, Randomized, Investigator and Patient-blind, Sponsor-unblinded, Parallel Group, Placebo-controlled Study to Investigate the Safety, Tolerability, Pharmacokinetics, and Pharmacodynamics of ATI-450 Plus Methotrexate (MTX) vs MTX Alone in Patients with Moderate to Severe Active Rheumatoid Arthritis with Inadequate Response to MTX

Sponsor: Aclaris Therapeutics, Inc.

Study Phase: Phase 2a

Study Sites: [REDACTED]

Objectives and Endpoints:

Objectives		Endpoints
Primary	
 To assess the safety and tolerability of ATI-450 plus MTX in patients with moderate to severe rheumatoid arthritis (RA) 	
 Number and percent of adverse events (AEs) and serious adverse events (SAEs); mean change from baseline in laboratory values, vital signs, and electrocardiograms (ECGs)
Secondary	
 To assess the pharmacodynamics (PD) of ATI-450 plus MTX in patients with moderate to severe RA 	
 Median percent change from baseline in high sensitivity C-reactive protein (hsCRP) levels over time Mean change from baseline in Disease Activity Score using 28 joint count-C-reactive protein (CRP) (DAS28-CRP) over time Proportion of patients with DAS28-CRP below 2.6 Mean change from baseline in Rheumatoid Arthritis Magnetic Resonance Imaging Score (RAMRIS) Hand-Wrist assessments of synovitis or osteitis at Week 12 Proportion of patients with American College of Rheumatology (ACR)20/50/70 over time
	
 To assess the pharmacokinetics (PK) of ATI-450 in patients with moderate to severe RA who are receiving concomitant MTX 	
 ATI-450 concentrations at trough and 2 hours post-dose

Exploratory	
 • To assess the PD of ATI-450 plus MTX in patients with moderate to severe RA 	
 • Mean change from baseline in endogenous cytokine levels (e.g., tumor necrosis factor-α [TNF-α], interleukin [IL]-1β, IL-6, IL-8, IFNγ, IL-17, IL-18, IL-10, IL-1α and IL-1RA) • Mean change from pre-dose in ex vivo stimulated cytokine levels (e.g., TNF-α, IL-1β, IL-6, IL-8, IFNγ, IL-17, IL-18, IL-10, IL-1RA, and IL-1α) • Ex vivo stimulated phosphoprotein modulation • Mean change from baseline in the cartilage loss score (CARLOS) Hand-Wrist magnetic resonance imaging (MRI) assessment of cartilage loss
--------------------	---------------------------------------------------------------------------------------------------------------------------------	------------------------------------------------------------------------------------------------------------------------------------------------------------------------------------------------------------------------------------------------------------------------------------------------------------------------------------------------------------------------------------------------------------------------------------------------------------------------------------------------------------------------------------------------------------------------------------------------------------------------------------------------------------------------------------------------------------------------------------------------------------------------

Study Design:

This is a Phase 2, randomized, investigator and patient-blind, sponsor-unblinded, parallel group, placebo-controlled study to investigate the safety, tolerability, PK, and PD of ATI-450 plus MTX versus MTX alone in patients with moderate to severe RA.

The study will consist of an up to 28-day screening period, a 12-week treatment period, and a 4-week follow-up period. The total duration of the study for patients remaining until their final follow-up assessment will be up to 20 weeks.

The investigator will obtain signed informed consent from the patient before any study procedures are performed.

During the screening period, each patient will be required to have all assessments performed as outlined in the Schedule of Assessments. The MRI is not to be performed until the site obtains the results of the patient's hsCRP level to ensure that this assessment meets the entry criteria prior to performing the MRI. The patient will have the RAMRIS Hand-Wrist MRI assessment performed at their local institution and evaluated by a central radiology review team to determine if they meet the radiological inclusion criteria. Results for all of the screening assessments must be available at the time patient eligibility is reconfirmed prior to randomization and dosing.

Patients whose eligibility is confirmed at baseline will be randomized in a 3:1 ratio to receive either ATI-450 tablets (50 mg twice daily [BID]) plus MTX, or matching placebo tablets plus MTX. Study medications will be administered orally for 12 weeks. Patients will be required to remain on a stable dose of MTX (7.5 mg to 25 mg/week) for the duration of the study.

Patients will attend clinic visits on Days 7, 14, 28, 42, 56, and 84 (± 1 day) for safety, efficacy, PK, and PD assessments. The morning dose of study medication will be administered in the clinic on each study visit day.

At the completion of 4 weeks of treatment (Day 28), each patient's safety data (e.g., AEs, laboratory values, vital signs, and ECGs) will be reviewed by the Aclaris medical monitor and Aclaris safety physician to ensure that the patient is tolerating the treatment regimen and is deemed suitable to continue treatment for the next 8 weeks.

On Day 84 (Week 12), patients will complete the end of study assessments. A safety follow-up visit will be conducted 30 days (+7) after the last dose of study medication.

The study is randomized and blinded to the investigator, patient, site personnel, and sponsor representatives responsible for clinical monitoring at the investigational to prevent bias in treatment allocation and in the assessment of treatment effect. The Aclaris statistician, medical and safety monitor will be unblinded to each patient's treatment assignment.

Study Duration:

The start of the study will be the date on which the first patient provides informed consent, and the end of the study will be the date of the last patient's last assessment.

Planned Number of Patients: It is planned to enroll 25 patients in order to obtain 15 evaluable patients. An evaluable patient is a patient who meets all entry criteria and completes 12 weeks of treatment.

Target Population:**Inclusion Criteria**

Patients must meet the following criteria to be eligible for participation in the study:

1. Able to comprehend and be willing to sign the Institutional Review Board (IRB)-approved subject informed consent form (ICF) prior to administration of any study-related procedures.
2. Diagnosis of adult-onset RA as defined by the 2010 American College of Rheumatology/European League Against Rheumatism (ACR/EULAR) classification criteria.
[REDACTED]
[REDACTED]
[REDACTED]
6. Patients must have definitive intra-articular synovitis or osteitis defined as a score of 1 or greater on a Hand-Wrist MRI as assessed by central imaging reader (using RAMRIS).
7. On a stable MTX dose (defined as 7.5 mg to 25 mg weekly) and a stable dose of folic or folinic acid (defined as \geq 5mg/week) for at least 4 weeks prior to the screening visit.
8. Male or non-pregnant, non-nursing female patients between 18 and 70 years of age, inclusive.
 - Female patients who are of childbearing potential must use 2 methods of highly effective contraception* - one of which must be a physical barrier- for the duration of the study and for 30 days after the last dose
 - Male patients of childbearing potential with a female partner of childbearing potential must agree to use a condom plus another highly effective form of birth control for the duration of the study and for 90 days after the last dose
9. Female patients must have a negative serum pregnancy test at screening and a negative urine pregnancy test prior to dosing on Day 1.
10. Screening laboratory evaluations (hematology, chemistry, coagulation, and urinalysis) must fall within the normal range of the central laboratory's reference ranges unless the results have been determined by the investigator to not be clinically significant.
11. Willing and capable of taking appropriate coronavirus disease 2019 (COVID-19) risk mitigation precautions (e.g., wearing a mask in public, adhering to social distancing, etc.) as recommended or required by local, state, or federal guidelines during participation in the study.

*Highly effective birth control is defined as those which result in a low failure rate (i.e., less than 1% per year) when used consistently and correctly such as implants, injectables, combined oral contraceptives, some intrauterine devices, heterosexual abstinence, or vasectomized. The requirements for highly effective birth control do not apply to female patients of nonchildbearing potential (i.e., physiologically incapable of becoming pregnant) defined as:

- Has had a complete hysterectomy greater than or equal to 3 months prior to dosing or
- Has had a bilateral oophorectomy (ovariectomy) or
- Has had a bilateral tubal ligation or fallopian tube inserts or
- Is postmenopausal (i.e., cessation of regular menses for at least 12 consecutive months with no alternative pathological or physiological cause and have a serum follicle-stimulating hormone (FSH) level >40 mIU/mL) or
- Medically documented ovarian failure

Exclusion Criteria

A patient who meets any of the following exclusion criteria will not be eligible for inclusion in the study:

1. Patient has a current acute or chronic immunoinflammatory disease other than RA which may impact the course or assessment of RA.
2. Patient has an uncontrolled non-immunoinflammatory disease that may place the patient at increased risk during the study or impact the interpretation of results.
3. History or evidence of active or latent tuberculosis.
4. Known hypersensitivity to MTX or ATI-450.
5. Patient has a history of either alcoholism/current alcoholic, alcoholic liver disease, or other chronic liver disease.
6. Active infection requiring treatment with antibiotics.
7. Positive for HIV, hepatitis B or C. Patients with serologic evidence of hepatitis B vaccination (hepatitis B surface antibody without the presence of hepatitis B surface antigen) will be allowed to participate.
8. Tests performed at a central laboratory at screening that meet any of the criteria below (out of range labs may be rechecked one time, after consultation with sponsor or designee, before patient is considered a screen failure):
 - White blood cell count $<3.0 \times 10^3$ cells/mm³
 - Absolute neutrophil count $<1.5 \times 10^3$ cells/mm³
 - Lymphocyte count $<0.5 \times 10^3$ cells/mm³
 - Platelet count $<100 \times 10^3$ cells/mm³
 - Hemoglobin <10 g/dL
 - Aspartate aminotransferase (AST) or alanine aminotransferase (ALT) $\geq 1.5 \times$ upper limit of normal (ULN)

- Total bilirubin level $\geq 2 \times \text{ULN}$ unless patient has been diagnosed with Gilberts' disease and this is clearly documented
- Estimated glomerular filtration rate (eGFR), $< 40 \text{ mL/min/1.73 m}^2$ based on Modification of Diet and Renal Disease formula

9. Any clinically significant laboratory abnormality that would affect interpretation of study data or safety of the patient's participation in the study, per judgment of the investigator.
10. Patient has clinically significant abnormal findings other than RA from physical examination conducted at screening visit (Visit 1) and at baseline visit (Visit 2) that may affect the interpretation of study data or the safety of the patient's participation in the study, per the judgment of the investigator.
11. Patient has a clinically important history of a medical disorder that would compromise patient safety or data quality (per investigator's judgment).
12. Blood pressure levels (in supine position after at least 5 minutes rest): $< 90 \text{ mmHg}$ or $> 140 \text{ mmHg}$ for systolic blood pressure or $< 40 \text{ mmHg}$ or $> 90 \text{ mmHg}$ for diastolic blood pressure.
13. [REDACTED]
14. Are currently receiving corticosteroids at doses greater than 10 mg per day of prednisone (or equivalent) or have been receiving an unstable dosing regimen of corticosteroids within 2 weeks of the screening visit.
15. Have started treatment with non-steroidal anti-inflammatory drugs (NSAIDs) or have been receiving an unstable dosing regimen of NSAIDs within 2 weeks of the screening visit.
16. Patients with history of stroke.
17. Significant cardiac disease that would affect interpretation of study data or the safety of the patient's participation in the study, per judgment of the investigator, including recent myocardial infarction or unstable angina, or heart failure with New York Heart Association Class III or IV symptoms.
18. Patients with the following screening or pre-dose ECG findings, specifically:

- Evidence of atrial fibrillation, atrial flutter, complete right or left bundle branch block, Wolff-Parkinson-White Syndrome, or other significant rhythm disturbance
- Evidence of acute ischemia
- Screening or pre-dose baseline mean QTcF >450 msec for males or >470 msec for females (use of the ECG algorithm is acceptable for this purpose)
- Personal or family history of congenital long QT syndrome or sudden death
- Any other finding that is considered clinically significant

19. Any joint procedure in the past 90 days prior to screening.
20. Known exposure to an individual with a confirmed diagnosis of COVID-19 at any time during the screening period.
21. Vaccination with a live or attenuated vaccine within 6 weeks prior to Baseline (Visit 2) or planned vaccination with these vaccines at any time during treatment or within 6 weeks following discontinuation of study medication.

Test Product:

Name: ATI-450 (50 mg)

Dose: 50 mg BID

Mode of administration: Oral tablets

Concomitant Product

Name: Methotrexate (MTX)

Dose: Patients are to remain on their stable dose of MTX (defined as 7.5 mg to 25 mg per week) throughout the 12-week treatment period

Mode of administration: Oral tablets

Control Product:

Name: Placebo

Dose: 0 mg; administered BID

Mode of administration: Oral tablets

Statistical Methods:

Details of all statistical summaries will be provided in the study-specific statistical analysis plan (SAP).

Analyses will be performed using SAS® (SAS Institute, Cary, NC, US) by the sponsor or its representatives.

The SAP will be approved prior to any lock of the study database and unblinding of the study data. The SAP will provide a detailed description of the statistical methods and expand on the details provided in the protocol.

All data will be presented by treatment group. Descriptive statistics (number of observations, mean, standard deviation, median, minimum, and maximum) will be provided for continuous variables, and counts and percentages will be presented for categorical variables.

Baseline is defined as the last non-missing measurement before or on the date of first administration of study medication.

Determination of Sample Size

The sample size for this study was determined based upon feasibility constraints as opposed to a formal power computation. Approximately 25 patients are planned to be enrolled with the expectation that at least 15 patients will complete the 12-weeks of treatment.

Interim Analyses

This study is being conducted as a sponsor-unblinded study. The safety and efficacy will be assessed on an ongoing basis during the conduct of the trial via multiple unblinded interim analyses. The frequency of the interim analyses will be approximately weekly depending upon the rate of enrollment. Since there is no formal statistical hypothesis, there will be no alpha spending adjustment made for multiple analyses. There is no scenario for which the study would be stopped early for efficacy.

Analysis Populations

- The Safety population will include all patients who have been administered at least one dose of study medication.
- The Intent-to-treat (ITT) population will include all randomized patients.
- The Per-Protocol population will include all patients who have completed their Day 84 visit and have valid hsCRP values for at least 6 of the 7 scheduled collection times.
- The PK population will include all patients who receive at least 1 dose of ATI-450 and provide at least one plasma concentration value.

Efficacy Analyses

All efficacy summaries will be conducted on both the ITT and Per-Protocol populations.

- The hsCRP levels, change from baseline in hsCRP and percent change from baseline in hsCRP will be summarized over time using continuous statistical summary measures. Determination of sustained treatment effect for hsCRP will be based upon the median percent change from baseline in hsCRP over time in the Per-Protocol population.
- The DAS28-CRP, RAMRIS and CARLOS Hand Assessments, 66/68 swollen/tender joint count, Patient's Global Assessment of Disease Activity, Patient's Assessment of Arthritis Pain, and Physicians Global Assessment of Disease Activity, as well as their corresponding changes from baseline will be summarized over time (for all scheduled timepoints) using continuous statistical summary measures. The focus of the MRI analyses will be the synovitis and osteitis scores.
- The number and proportion of patients with DAS28-CRP <2.6 and the number and proportion of patients meeting American College of Rheumatology (ACR) 20/50/70 will be tabulated at each scheduled visit, separately.

Safety Analyses

The Safety population will be used for the analysis of safety data (AEs, exposure to study medication, clinical laboratory values, vital signs, and ECG).

AEs will be coded with the Medical Dictionary for Regulatory Activities (MedDRA). Treatment-emergent adverse events (TEAEs) are defined as AEs with an onset date on or after the date of first administration of study medication and through the completion of the last follow up visit or the date of last administration of study medication + 30 days (whichever occurs later). TEAEs will be presented by system organ class and preferred term in frequency tables. Patients with multiple AEs will be counted

only once within each preferred term and system organ class. Key patient information for patients with an AE with an outcome of death, patients with SAEs, and patients with an AE leading to discontinuation of study medication will be listed.

Laboratory data (hematology, serum chemistry, coagulation, and urinalysis) will be converted to Système International units for reporting and processing purposes. Absolute values and changes from baseline will be presented descriptively. Laboratory data outside study specific reference ranges will be listed. Vital signs and ECG parameters will be presented descriptively.

ATI-450 Drug Concentrations and Pharmacokinetic Analyses

Plasma concentrations of ATI-450 will be summarized by nominal timepoint and day. Trough concentration versus time (Days 7, 14, 28, 42, 56, and 84) and concentration versus time (0 and 2 hours post-dose) by day (Days 1 and 84) will be displayed by linear scale.

Pharmacodynamic Analyses

The assessment of cytokines and phosphoprotein PD parameters will be described and provided in a separate report(s).

Protocol version and date: 3.0, 27July2020

SCHEDULE OF ASSESSMENTS

Table 1 Schedule of Assessments

Assessment	Screening Visit 1 Day -28 to Day -1	Visit 2 Baseline Day 1	Visit 3 Day 7	Visit 4 Day 14	Visit 5 Day 28	Visit 6 Day 42	Visit 7 Day 56	Visit 8 Day 84 (Week 12)	Visit 9 Follow-up 30 days (+ 7 days)		
			+/-1 day								
Informed Consent	X										
Eligibility Review	X	X									
RA and Other Medical History and Demographics	X										
QuantiFERON Gold Test for TB	X										
Height	X										
Weight	X								X		
Full Physical Exam ¹	X							X	X		
Limited Physical Exam		X	X	X	X	X	X				
	█	█	█	█	█	█	█	█	█		
	█	█	█	█	█	█	█	█	█		
SARS-CoV-2 Testing by RT-PCR		X									
HIV and Hep Screen	X										
Vital Signs	X	X	X	X	X	X	X	X	X		
12-Lead ECG	X	X			X			X	X		
Hematology, Coagulation, Chemistry, Lipids, and Urinalysis	X	X	X	X	X	X	X	X	X		
hsCRP	X	X	X	X	X	X	X	X	X		
	█	█	█	█	█	█	█	█			

Assessment	Screening Visit 1 Day -28 to Day -1	Visit 2 Baseline Day 1	Visit 3 Day 7	Visit 4 Day 14	Visit 5 Day 28	Visit 6 Day 42	Visit 7 Day 56	Visit 8 Day 84 (Week 12)	Visit 9 Follow-up 30 days (+ 7 days)
[REDACTED]		[REDACTED]	[REDACTED]	[REDACTED]	[REDACTED]	[REDACTED]	[REDACTED]	[REDACTED]	[REDACTED]
RAMRIS and CARLOS Hand-Wrist MRI Assessments	X ⁶							X ¹⁰	
[REDACTED]	[REDACTED]	[REDACTED]	[REDACTED]	[REDACTED]	[REDACTED]	[REDACTED]	[REDACTED]	[REDACTED]	[REDACTED]

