1.2 Study Rationale

The assessment of 12-weeks of ATI-450 exposure in patients with RA will provide important data to initially describe the safety and tolerability of ATI-450 in a relevant patient population.

The p38 MAPK pathway offers great potential in the treatment of inflammatory diseases such as RA. Unfortunately, this potential has not been realized in clinical studies where it has been hypothesized that the lack of efficacy resulted from the development of tachyphylaxis.^{1, 2, 3}

The tachyphylaxis hypothesis has been supported by the consistent observation in the studies cited above, that C-reactive protein (CRP) showed an initial rapid reduction, followed by a return to baseline within 4 to 8 weeks. It is thought this may be a result of p38 MAPK inhibitors inhibiting anti-inflammatory downstream substrates in addition to proinflammatory substrates.

By targeting MK2, which is downstream from p38, it is believed that ATI-450 can inhibit the inflammatory pathways without a significant impact on anti-inflammatory pathways, which could lead to the avoidance of tachyphylaxis. This hypothesis is supported by pre-clinical models.

The consistent pattern of CRP tachyphylaxis with p38 inhibition provides an efficient model to test the potential of MK2 inhibition to avoid tachyphylaxis, i.e., if a reduction in CRP is achieved and maintained over 12 weeks, MK2 inhibition will have been shown to have a PD profile that is distinct from p38 inhibition and one that could offer potential for efficacy in RA. This study will assess the CRP profile.

This study is being conducted to determine the safety, tolerability, PK, PD and preliminary efficacy of ATI-450 in combination with MTX in patients with moderate to severe RA. The results of this study may benefit patients with RA.

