3.2 Discussion of Study Design

The study is designed to assess the safety and tolerability of ATI-450 in a relevant patient population (i.e., patients with RA).

The study will also describe the PK and PD of ATI-450 in a relevant disease. The efficacy hypothesis to be explored is described in [Section 1.2](#) and provides justification for recruiting a population with active RA and elevated hsCRP.

Investigator and patient blinding will maintain integrity for assessments of safety and AEs. The 3:1 randomization schedule will maximize the number of patients receiving active drug to allow for a more robust assessment for the change from baseline in hsCRP.

The 12-week treatment period is sufficient to explore the tachyphylaxis signal (observed within that timeframe by p38 MAPK inhibitors). Treatment of all patients with MTX ensures that all patients will receive active treatment for their RA throughout the study.

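### As far as the text is readable, a sustained hsCRP effect is judged from Per-Protocol visit medians with no measure of precision; two within-patient ratios with 95% intervals would be a cheap improvement

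*Combined protocol and SAP*

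**What the plan says.** The Protocol Summary (Efficacy Analyses) states: "Determination of sustained treatment effect for hsCRP will be based upon the median percent change from baseline in hsCRP over time". It ties this determination to the Per-Protocol population, which requires a completed Day 84 visit and valid hsCRP at 6 or more of 7 collection times. Summaries are broader than the determination: "All efficacy summaries will be conducted on both the ITT and Per-Protocol populations".

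The statistics named in the Protocol Summary and in Section 8.1 are: "Descriptive statistics (number of observations, mean, standard deviation, median, minimum, and maximum) will be provided for continuous variables". I find no interval, no late-versus-early measure and no numerical meaning of sustained.

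Section 1.2 states the question. Earlier p38 inhibitors gave a rapid CRP fall "followed by a return to baseline within 4 to 8 weeks"; by contrast, "if a reduction in CRP is achieved and maintained over 12 weeks, MK2 inhibition will have been shown to have a PD profile" distinct from p38 inhibition. Section 3.2 links the study length to this: "The 12-week treatment period is sufficient to explore the tachyphylaxis signal".

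The sample size is feasibility-based and no formal hypothesis is stated. The efficacy text of Section 8.4 is blacked out, and the SAP to which details are deferred is not in the text supplied.

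**The concern.** Whether the CRP fall lasts is the efficacy question of this study. The answer is to come from a row of medians, probably of about 11 treated patients. A median series shows the direction of travel but not its uncertainty. A weakening of 10 points may be noise, and a flat series may still be compatible with an appreciable loss of effect. Section 1.2 goes further than description when it says that a maintained reduction will have shown a distinct profile. A conclusion in those terms needs a statement of what the data exclude. Without one, a modest result could be read either as proof of durability or as early tachyphylaxis, and the report would offer no means of choosing.

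**Working it through.** The plan gives no power or precision figure, so there is none to reproduce.

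**Inputs from the protocol.** Enrolment 25, at least 15 completers, allocation 3:1, visits on Days 7, 14, 28, 42, 56 and 84. Active arm: 15 × 0.75 = 11.25, about 11 completers; 25 × 0.75 = 18.75, about 19 enrolled. Placebo: 15 × 0.25 = 3.75, about 4; 25 × 0.25 = 6.25, about 6.

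**Assumed, because the protocol gives no figure.** Early fall 60% (sensitivity 40%). Within-patient visit-to-visit SD of log hsCRP, s = 0.5 to 1.0. Rebounding patients return fully to baseline by Day 42 or Day 56. Simulations used 20,000 trials per setting. Early is the mean log of Days 7 and 14, late the mean log of Days 56 and 84, baseline one Day 1 value.

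**Step 1: the planned medians (n = 11, 60% fall).** Weakening means that the late medians lie at least 10 points above the early ones.
- Every patient returns to baseline: weakening in 99-100% of trials at s = 0.5-0.7, and 96% at s = 1.0.
- Nobody rebounds: weakening still appears in 12-21% at s = 0.5-0.7.
- 5 of 11 return: late median about -39%, weakening in 74-81%, and all six visit medians still negative in 76-93% (s = 0.5-0.7).

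**Step 2: ratio (a), late/early within patient.** The log difference has variance s²/2 + s²/2 = s². The 95% interval is the estimate multiplied and divided by exp(t × s/√n), with t = 2.228 at n = 11.

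**Step 3: ratio (b), late/baseline within patient.** The variance is s²/2 + s² = 1.5s², so the factor is exp(t × 1.225 × s/√n). With the effect maintained, the chance that the upper limit lies below 1 follows from the noncentral t distribution with noncentrality ln(1/(1 - fall)) ÷ (1.225 × s/√n). For example, at s = 1.0 and a 60% fall: 0.916 ÷ 0.369 = 2.48, giving 61%.

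| n = 11 | s = 0.5 | s = 0.7 | s = 1.0 |
|---|---|---|---|
| Factor for (a) | 1.40 | 1.60 | 1.96 |
| Factor for (b) | 1.51 | 1.78 | 2.28 |
| (b) excludes return, 60% fall | 99% | 89% | 61% |
| (b) excludes return, 40% fall | 70-71% | 43% | 24% |

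**Step 4: why (b) is needed.** After a 60% fall, a full return means (a) = 1/0.4 = 2.5. Comparing the upper limit of (a) with 2.5 as if it were known gives exclusion in 97-100% of trials at s = 0.5-0.7. But 2.5 is itself estimated from the same patients' Day 1 and early values. Ratio (b) carries that uncertainty and gives the honest 89-99%.

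**Step 5: partial rebound, 5 of 11.** The true (a) is 2.5^(5/11) = 1.52 and the true (b) is 0.4^(6/11) = 0.61. The lower limit of (a) exceeds 1 in only about 18-42% of trials over s = 0.5-1.0. Its upper limit falls below 2.5 in about 25-61%. Ratio (b) speaks only of the arm average. Neither interval settles this case.

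**Step 6: placebo contrast.** The factor is exp(t × SD × √(1/11 + 1/4)) with t = 2.179 on 12 degrees of freedom: 2.15 at a log-change SD of 0.6 and 4.60 at 1.2. This is too wide to carry weight.

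**The case against.** The strongest reply is that nothing here is an error. The study is a feasibility-sized Phase 2a trial with safety as its primary objective, and hsCRP is a secondary endpoint defined as a median percent change. Section 3.2 speaks of exploring, and Section 1.2 is conditional in form. All of that stands, and it is why this is an improvement and not a defect.

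A reader might infer that the planned medians would miss tachyphylaxis. They would not, if it takes the form Section 1.2 describes. Step 1 shows a whole-arm return is nearly always visible. At s = 1.0 the medians even do better than ratio (a), whose lower limit exceeds 1 in 79% of such trials against 96% for the medians' 10-point rule. Partial rebound is a scenario of this review, not of the protocol, and the proposed intervals do not resolve it.

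A reader might also infer that the meaning of maintained will be chosen after the data are seen, since "The safety and efficacy will be assessed on an ongoing basis during the conduct of the trial via multiple unblinded interim analyses". The text does not support that. It also says "The SAP will be approved prior to any lock of the study database and unblinding of the study data", and a definition may exist in the unseen SAP. The frequent unblinded looks are a reason to place the estimates in that SAP; they are not evidence of after-the-fact choice.

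Finally, means, SDs, minima and maxima by arm in both populations will show some spread. They summarise each visit separately, however, and the listed statistics include no within-patient interval.

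**Conclusion.** The point holds as a cheap improvement. In the readable text, the basis for declaring a sustained hsCRP effect has no measure of precision, while Section 1.2 attaches a firm conclusion to it. The gain from the added ratios is a statement of what the data exclude, not better detection of a whole-arm return.

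That gain is real but limited. At n = 11 the late/early ratio is known to within a factor of 1.4 to 2.0. Exclusion of a return to baseline is likely after a large maintained fall (61-99%) and uncertain after a moderate one (24-71%). If all 19 enrolled active patients contributed, the late/early factor would be 1.27 at s = 0.5 and 1.40 at s = 0.7.

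All SDs, falls and rebound fractions are assumptions. The conclusion also depends on text that cannot be read: if the redacted Section 8.4 or the SAP already holds such an estimate, nothing remains of the point.

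**What to change.** Keep the medians as planned. In the SAP, add as pre-specified estimates and not tests, for the ATI-450 arm in both Per-Protocol and ITT:

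- (a) the geometric mean within-patient ratio of Day 56/84 to Day 7/14 hsCRP, with 95% interval;
- (b) the geometric mean within-patient ratio of Day 56/84 to baseline hsCRP, with 95% interval.

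Judge whether hsCRP has stayed below baseline from (b), not by setting (a) against a fixed benchmark. Name the early and late visits in advance. State what is done when an early or late value is missing, since the Per-Protocol definition tolerates one missing value in seven, and report how many ITT patients lack one. Section 4.4.1 already asks for Day 84 assessments after early stopping of study medication, so some of those patients will have a late value. Show placebo descriptively alongside; a baseline-adjusted placebo contrast and a count of patients back at baseline are optional. Word the Section 1.2 inference so that it claims no more than the intervals support.

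The cost is SAP wording and a few lines of code on samples already scheduled, with no new patients or visits. The drawback is that the intervals will be wide and may look less favourable than a median alone.
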